5.1 Indications

- Primary or secondary arthrosis,
- Advanced joint destruction resulting from rheumatoid arthritis or traumatic arthritis,
- A fracture or an avascular necrosis,
- Following a previous surgical operation, on condition that the new device does not interfere with the material in place.
- Displaced sub-capital or transcervical fracture as well as stages I and IIB bone loss according to the PAPROSKY classification.
- bone loss classifications of SOFCOT stages I to VI, PAPROSKY types I to VI and the AAOS types Ia to Ic.

5.2 Target population:

Adult patients presenting a pathology necessitating a surgical intervention for joint replacement or a surgical revision of a hemiarthroplasty or a total hip arthroplasty.

5.3 Contraindications

Contra-indications and conditions with higher risk of failure:

- Local or systemic acute or chronic infections (heart disease, uncompensated diabetes, regular hemodialysis, impairment of the immune system, etc.),
- Severe muscular, neurological or vascular deficiencies affecting the extremity concerned,
- Destruction, loss or poor bone quality that could affect the stability of the implant, severe osteoporosis, serious deformation of the joint that needs replacing,
- Any associated disorder that could compromise the function or the implantation of the prosthesis,
- Systemic or metabolic issues,
- A patient's intellectual incapacity to understand the surgeon's instructions,
- Addiction to drugs, alcohol, smoking or medication,
- Local bone tumours,
- Obesity, excess weight, intense activity, intensive sports training, falls,
- Size 1 Sagitta EVL-R® SCC and Sagitta EVL-R® SCS stems must only be used on patients weighing less than 55 kg,
- Size 2 Sagitta EVL-R® SCC, Sagitta EVL-R® SCS and Sagitta EVL-R® SCL stems must only be used on patients weighing less than 70 kg.

6 STUDY OBJECTIVES

The use of femoral stems without cement is known to give long terms satisfying clinical results. In these cases, the sagitta EVL-R stems are especially used for severe traumas of the femur and mainly for revision of arthroplasties for any reason whatsoever, respecting indications of the IFU. The extended and osseointegration of these implants were reported in numerous series, despite the use of stems with many different shapes a, macrostructures, coating repartition materials differences and with or without potentially with additional fixation. This study is attempting to provide further clinical data on this medical device for the post market clinical follow up. It will implement the knowledge of this device concerning its performance and its safety according to the directive 93/42/EEC. The results of this study will be used for marketing supports, conference papers and/or scientific article if possible, and as a basis for claimed current indications for the device.

6.1 Primary objective

The primary objective is to assess the significant clinical impact on patients treated for a total hip arthroplasty at **their last** follow-up (between 5 to 8 years) after surgery as a performance criterion.

6.2 Secondary objectives:

Preoperative clinical medical and surgical history will be harvested (Principal medical and surgical history, concomitant treatments if significative for the assessment of the pathology/treatment) to estimate the impact of comorbidity and risks factors on the pathology, and its reparation over time.

| | | | |
|--|------------------------------|---|--------------------------------|
|  serf | Document No. | SAGITTA EVL-R STEMS – NOVAE / SAGITTA EVL-R CUPS | ID RCB : 2019-A01777-50 |
| | 2019-10-EVLR-N Version 02 | | |
| | | | Page No. Page 16 sur 28 |

Postoperative Functional improvement periods following a total hip arthroplasty.

Postoperative Radiological assessment of the reparation through pictures of the cotyles (face view) and femurs (face and profile views). The goals are to see the evolution of the reparation and moreover the interface behavior between prothesis and surrounding tissues; and if there's no displacement of the stems or more globally to the assembly along time.

- The face radiography of the femur and therefore of the stem will be appreciated to estimate a potential subsidence between the immediate postoperative period and middle term / long terms postoperative periods. This subsidence can potentially be a primary step to a loosening. The radiolucent line will be appreciated to emphasize of radiological level of loosening. This finding may have no clinical impact on the patient daily life. It will depend of the level of loosening of the cup and its evolution. Generally, a clinical impact is regularly associated with failure and/or pain; thus necessitating a surgical revision. Tangsatapron et al. have analyzed that risks factors inducing femoral stem subsidence were the weight of patients and long sizes of stems and more particularly a medial-lateral stem-bicortical fit less than 2cm (Tangsataporn et al. 2015). Ries et al. have shown that the subsidence was statistically higher in patients collarless stems than with collar (Ries et al. 2019). Girard et al. have emphasized that the bad quality of the osseointegration of the stem is risk factor for subsidence (Girard et al. 2011).
- As well as the face femur picture, the profile view of the femur would inform (in another dimension) about a potential subsidence / or a radiolucent line confirming a radiological and/or a clinical loosening of stem, that can lead to a surgical revision.
- The face radiography of the cotyle will mainly measured the inclination of the implant and its stability over time through its migration. The radiolucent line will be appreciated (De LEE and Charnley scales) to emphasize of potential radiological level of loosening. This finding may have no clinical impact on the patient daily life. It will depend of the level of loosening of the cup and its evolution.

The daily physical activity will be harvested postoperatively to see the incidence of the reparation of the patient daily autonomy at their last timepoints.

The co-morbidity will be measured preoperatively and postoperatively using the Charnley classification. The goal is to estimate if the co-morbidity may be detrimental to the clinical results and their evolution and potentially to identify the nature of detrimental factors.

All complications will be recorded during the study. A global survival rate would therefore be calculated at each timepoints. As the same manner, an aseptic loosening rate and a global complication rate will be evaluated. Other specific complication rate would be evaluated is considered representative and pertinent.

The global satisfaction of patients will be measured at the last postoperative timepoints.

The walking ability will be measured at the last postoperative timepoints.

The global functional improvement will be measured at the last postoperative timepoints.

The pain release will be estimated at the last postoperative timepoints.

The length of the operated limb will be harvested to see if the chosen assembly was adequate and to see its evolution over time.

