| Study visits | 
There's no inclusion period because of the retro-prospective design of the study. Only a phone call will be performed following the start of the data collection. The data collection would be performed during 2 to 4 8 to 10 consecutive days, depending of the ease to consult patient files.
 
Duration of the follow-up period for each patient: until a maximum of 8 years postoperatively. In fact, operated patients between 2011 and 2014 in a single center will be potentially eligible. Therefore, the maximum follow-up through a phone call will be between 5 to 8 years.
 
Patients will be followed at 2 stages: through their medical files (pre-operative, per-operative, immediate post-operative and postoperative follow-up), and between 5 to 8 years after implantation through a single phone call.
 |
| Study population | 
Constitution and follow-up of a cohort of patients operated for a primary total hip arthroplasty or a revision of hemiarthroplasty or total hip arthroplasty with implantation of
 |

the sagitta EVL-R femoral stem at a minimum. Most of time, several implants of the assembly are changed in case of revision. In case of primary surgical intervention, a stem + head and intermediate cup will be implanted for hemiarthroplasty; and a stem + head + insert + cup will be implanted for a total hip arthroplasty.

Inclusion criteria:

- Patients over 18 years old.
- Patients that were treated with the sagitta EVL-R stem for an indication of arthroplasty and according to the Instruction For Use (IFU).
 - Primary or secondary arthrosis,
 - Advanced joint destruction resulting from rheumatoid arthritis or traumatic arthritis,
 - A fracture or an avascular necrosis,
 - Following a previous surgical operation, on condition that the new device does not interfere with the material in place.
 - indicated in the case of primary or secondary arthrosis, displaced sub-capital or transcervical fracture as well as stages I and IIB bone loss according to the PAPROWSKI classification.
 - The SAGITTA EVOLUTION for REVISION implant is recommended for indications according to the bone loss classifications of SOFCOT stages I to VI, PAPROSKY types I to VI and the AAOS types Ia to Ic.
 - Dysplasia
- Patient being informed to the study and non-opposed of its participation and the use its pertaining data.
- Patients with a minimum follow up of 24 months.

Non-inclusion criteria:

- Patient presenting a contraindication indicated in the IFU.

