6.3 Primary endpoint

The clinical improvement at the postoperative periods will be evaluated postoperatively at the last follow-up using through the validated Oxford Hip Score and with its primary interpretation. The Oxford Hip Score (OHS) is a short 12-item patient-reported PRO specifically designed and developed to assess function and pain with patients undergoing hip replacement surgery. It is short, reproducible, valid and sensitive to clinically important changes. The overall time needed to fill for the patient is about 5 to 7 minutes. There are a dozen of items. The score has a maximum of 60 points (worst possible outcome) and a minimum of 12 points (best possible score). The OHS is a patient self-completion PRO containing 12 questions on activities of daily living. The OHS has been developed and validated specifically to assess function and pain for patients undergoing total hip replacement (THR) surgery. The OHS is the most evaluated hip specific measure available.

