8.2 Inclusion criteria

The inclusion and exclusion criteria are controlling legal aspects of a clinical study in general; and the respect of indications cited in the instruction for use of the medical device. There's no other imposed restrictions.

The inclusion criteria are:

- Patients over 18 years old.
- Patients that were treated for an indication of arthroplasty and according to the Instruction For Use (IFU).
 - Primary or secondary arthrosis,
 - Advanced joint destruction resulting from rheumatoid arthritis or traumatic arthritis,
 - A fracture or an avascular necrosis,
 - Following a previous surgical operation, on condition that the new device does not interfere with the material in place.
 - indicated in the case of primary or secondary arthrosis, displaced sub-capital or transcervical fracture as well as stages I and IIB bone loss according to the PAPROWSKI classification.
 - The SAGITTA EVOLUTION for REVISION implant is recommended for indications according to the bone loss classifications of SOFCOT stages I to VI, PAPROSKY types I to VI and the AAOS types Ia to Ic.
 - Dysplasia
- Patient being informed to the study and non-opposed of its participation and the use its pertaining data.
- Patients with a minimum follow up of 24 months.

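### The primary objective names total hip arthroplasty patients, but the cohort also admits hemiarthroplasty, so a score pooled over all 120 may not describe the population in the objective

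*Protocol*

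**What the plan says.** **Objective and endpoint.** Protocol section 6.1 reads: "The primary objective is to assess the significant clinical impact on patients treated for a total hip arthroplasty at" their last follow-up, between 5 and 8 years. The Summary repeats this. The Summary's primary endpoint and the first item of section 6.4 both describe functional improvement after a total hip arthroplasty, measured by the Oxford Hip Score. Section 6.3 adds: "The OHS has been developed and validated specifically to assess function and pain for patients undergoing total hip replacement (THR) surgery".

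**Cohort.** The Summary (Study population) opens with: "Constitution and follow-up of a cohort of patients operated for a primary total hip arthroplasty or a revision of hemiarthroplasty or total hip arthroplasty with" the EVL-R stem. Two sentences later it says: "In case of primary surgical intervention, a stem + head and intermediate cup will be implanted for hemiarthroplasty", and then gives the components for a total arthroplasty. Section 5.2 defines the target population as: "Adult patients presenting a pathology necessitating a surgical intervention for joint replacement or a surgical revision of a hemiarthroplasty or a total hip arthroplasty". Section 8.2 admits: "Patients that were treated for an indication of arthroplasty and according to the Instruction For Use (IFU"), and says that nothing else restricts entry. The short title covers first-intention and revision arthroplasties.

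**Analysis.** Section 8.1 takes 120 consecutive patients, a number it calls arbitrary, as the base for calculation. Section 13.2 plans frequencies and percentages and a comparison of all data with the bibliography. It names no THA subset and no split by operation.

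**The concern.** The objective and the eligibility rules are both fixed in the protocol, and they name different populations. The Summary's population paragraph also disagrees with itself on whether primary hemiarthroplasty belongs in the cohort.

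This matters because the study has no control group. The only yardstick is published data, so the result means something only if the patients behind the score are of the same kind as those in the comparison. Sections 6 and 16.1 say that the results will support the device's claimed indications as well as marketing and publication. If the default is followed and all 120 are pooled, the headline score is reported for a group that the objective does not name. If a THA subset is used instead, the number of patients behind the primary result is unknown and may be well below 120.

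**Working it through.** **1. The plan's own figure.** The 120 cannot be reproduced. The Summary and section 8.1 call it arbitrary, and no effect size, standard deviation, power or dropout rate is given. There is no calculation to check, only the population to which the 120 refers.

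**2. The texts side by side.**

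| Place in the Protocol | Primary THA | Revision | Primary hemiarthroplasty |
|---|---|---|---|
| 6.1; Summary, primary objective | yes | can be read as included if a THA is treated | no |
| Summary, cohort sentence | yes | yes, of a hemiarthroplasty or a THA | not listed |
| Summary, component sentence | yes | – | yes |
| 5.2 Target population | yes | yes | yes (any joint replacement) |
| 8.2 Inclusion criteria | yes | yes | yes (any arthroplasty indication) |

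The objective does not say *primary*, so a patient whose THA was revised can fall within it. A hemiarthroplasty revised to a THA can as well. A patient left with a hemiarthroplasty after the index operation cannot.

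**3. Effect of pooling.** Let p be the share of the 120 with a THA after the index operation, m_T their mean score and m_O the mean of the others. Then

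pooled mean = p·m_T + (1 − p)·m_O, so pooled mean − m_T = (1 − p)·(m_O − m_T).

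**4. Effect of restricting to THA.** n = 120·p, and the 95% confidence half-width of a mean is 1.96/√n in SD units. This assumes that every patient has a score and that the normal approximation holds.

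The protocol does not give p, so the shares below are assumptions:

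| Assumed THA share | n in THA set | Half-width (SD) | Shift of pooled mean, as a fraction of the between-group difference |
|---|---|---|---|
| 100% | 120 | 1.96/√120 = 0.179 | 0 |
| 75% | 90 | 1.96/√90 = 0.207 | 0.25 |
| 50% | 60 | 1.96/√60 = 0.253 | 0.50 |
| 25% | 30 | 1.96/√30 = 0.358 | 0.75 |

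The protocol gives neither a standard deviation nor a between-group difference for the Oxford Hip Score, so none of this can be turned into score points.

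**The case against.** Several points on the other side are sound.

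- **Revisions.** A reader might infer that the cohort is mostly revisions, because section 6 says the stems are used "mainly for revision of arthroplasties for any reason whatsoever". That sentence describes how the stem is used in general. Nothing in the protocol gives the make-up of the 120, and a revised THA is not outside the objective.
- **Loose wording.** THA may be shorthand. Section 10.2 describes the recorded assembly as that of the THA, whatever the operation, and the cohort sentence lists no primary hemiarthroplasty. This makes a drafting slip plausible, but the component sentence and sections 5.2 and 8.2 still admit hemiarthroplasty.
- **Validity of the score.** Section 6.3 also says that the questionnaire was designed for hip replacement surgery in general. The narrower sentence on validation does not show that the score is unsuitable for hemiarthroplasty.
- **Size.** A reader might use the registry's 5-year revision rates in section 3.1, 2.5% for hemiarthroplasty and 4.3% for THA, to size the problem. They measure revision, not function. Their ratio also compares a cohort with no hemiarthroplasties to one made up entirely of them. They say nothing about a shift in the score.
- **Analysis plan.** Analysis sets and tables by operation are commonly left to a statistical analysis plan, and one may exist. Their absence is therefore not the finding. The finding is that the objective and the eligibility rules, both fixed in the protocol, disagree. Section 13.2 says that the protocol text already holds the main elements of the analysis plan, and nothing in that text resolves the conflict.
- **Recoverability.** Type of intervention (12.3) and assembly (10.2) are recorded, so a THA result can be extracted. It would therefore be too strong to infer that the study cannot answer its question.

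**Conclusion.** Wrong as written: the objective and the cohort contradict each other, and the Summary's population paragraph contradicts itself. The clear mismatch is hemiarthroplasty. Mixing primary and revision operations affects how the score is read, but is not a contradiction.

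Followed as it stands, the protocol leads to one pooled, uncontrolled score that may not describe the population in section 6.1. How far it departs depends on the case mix and on the difference in score between groups, and the documents give neither. If no hemiarthroplasty was in fact included, the consequence for the result disappears and only the wording needs repair. At assumed THA shares of 75% down to 25%, between a quarter and three quarters of the between-group difference enters the pooled mean. A THA-only result would rest on 90 down to 30 patients, with half-widths of 0.207 to 0.358 SD against 0.179 SD at 120. These are ranges under assumption, not estimates for this cohort.

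**What to change.** 1. In the Summary (Study population), reconcile the cohort sentence with the component sentence, so that it is clear whether primary hemiarthroplasty is in the cohort.
2. Make objective and cohort agree in one of two ways. Either reword section 6.1, section 6.4 and the matching Summary entries to *primary or revision hip arthroplasty with the EVL-R stem*, or keep the THA objective and define the primary analysis set as patients with a THA in place after the index operation.
3. In both cases, report the Oxford Hip Score by index operation (primary THA, hemiarthroplasty, revision), with the number of patients in each group, and compare each group only with literature on the same type of operation.

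The change costs wording and one table, since the data needed for the split are already collected. The drawback is that the subgroup estimates are less precise than a pooled figure.

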6.3 Primary endpoint

The clinical improvement at the postoperative periods will be evaluated postoperatively at the last follow-up using through the validated Oxford Hip Score and with its primary interpretation. The Oxford Hip Score (OHS) is a short 12-item patient-reported PRO specifically designed and developed to assess function and pain with patients undergoing hip replacement surgery. It is short, reproducible, valid and sensitive to clinically important changes. The overall time needed to fill for the patient is about 5 to 7 minutes. There are a dozen of items. The score has a maximum of 60 points (worst possible outcome) and a minimum of 12 points (best possible score). The OHS is a patient self-completion PRO containing 12 questions on activities of daily living. The OHS has been developed and validated specifically to assess function and pain for patients undergoing total hip replacement (THR) surgery. The OHS is the most evaluated hip specific measure available.

